Intravenous infusions by the Section of Investigative Medicine follow protocols established after extensive experience investigating the physiological role of numerous peptide hormones in humans. Single and combination infusion of gut hormones have been performed on large cohorts of human volunteers within this department without adverse event (ethics refs: 2002/6261 and 09/H0707/76).

This healthy human volunteer investigation will comply in full with the standard procedures that were developed at the behest of the RPMS ethics committee. This followed extensive discussion with a number of experts and their purpose is to ensure safety and efficacy in peptide preparation and administration. The procedures used in this study will be the same as those used in previous studies carried out by our group (ethics refs: 2002/6261 and 09/H0707/76).

Indirect calorimetry is a well-established technique in our laboratory. The calorimeter captures expired air from a large, transparent canopy, worn over the head and thorax, and is typically very well tolerated. Thermal imaging remotely measures the emission of infrared radiation from the surface of the skin using a small camera, does not involve ionizing radiation, and therefore does not expose the subjects to any additional risks.

¹⁸F-FDG PET-CT imaging is a well-established methodology and the Manov group has conducted a number of similar studies over the last 6 years. While PET studies involve additional ionizing radiation exposure for the participants, the levels of exposure from this study are in line with other experimental protocols conducted in healthy volunteers. We are proposing a T2* (echo planar) MR scanning protocol in a 3T scanner to perform fat extraction and MRI thermography. Magnetic resonance imaging is safe and widely used in clinical practice. It does not involve ionizing radiation.

METHOD FOR OBJECTIVE 1

To assess BAT activation in response to glucagon infusion in healthy volunteers using PET-CT, thermal imaging and MRI.

We have chosen one gut hormone, glucagon, to investigate using both thermal imaging, PET-CT and MRI. We have previously shown that glucagon induces a large rise in energy expenditure (EE) in healthy volunteers without any side effects³. To minimise radiation exposure, only volunteers who have a demonstrable rise in energy expenditure (EE) in response to glucagon infusion will undergo PET-CT scans.

Recruitment

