- Cumulative radiation exposure in the preceding 12 months totalling 10mSv or more.

*The lifetime risk for a healthy adult of developing a fatal malignancy following exposure to ionising radiation similar to that expected in our study is approximately 1:1800. This is low compared with the average UK cancer mortality rate of about 1 in 4, leading to a marginal added risk due to the study participation. However, higher BAT activation is expected in young adults⁴. We have therefore decided to enrol young adults in our study, in order to be able to demonstrate the principle of glucagon induced BAT activation in a small pilot study. Thus, while the risk e risk remains very small but is slightly greater in younger subjects. Given that only those subjects who have demonstrated significant rises in EE in response to glucagon would be put forward for PET-CT scanning, we expect to be able to achieve the aims of our study with a minimal number of subjects exposed to additional ionising radiation.

Study Visitsfor Objective 1

After the screening visit, volunteers will be invited to attend 7 study visits. There will be a time interval of at least two days between visits.

During Visit 1, 2 and 3, volunteers will receive an intravenous infusion of (A) saline under thermoneutral conditions, (B) saline with cold stimulationor(C) glucagon, allocated in a randomised single-blinded fashion. Resting and stimulated energy expenditure will be measured with a standard indirect calorimeter (as previously used successfully in this laboratory³). Supraclavicular deposits of BAT will be imaged using infrared thermography (i.e. thermal imaging).

If the volunteers have demonstrated a measurable rise in EE or BAT activation during these first 3 study visits, they will be asked to complete Visits4to 7. During Visit 4 and Visit 5, volunteers will receive an intravenous infusion of (A) saline or(B) glucagon, allocated in a randomised single-blinded fashion, and undergo a 60-minute dynamic FDG PET-CT scan.During Visit 6 and Visit 7, volunteers will receive an intravenous infusion of (A) saline (with cold stimulation) or (B) glucagon, allocated in a randomised single-blinded fashion, and undergo a 60-minute MRI scan.

Details of Study Visit Preparation, Blood Sampling, GlucagonInfusion, and Cold Stimulation.

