To minimise the usual hepatic glycogen depletion that occurs during an overnight fast, participants will be asked to avoid alcohol and strenuous exercise for 24 hours prior to each study visit, and to consume a high energy snack as late as possible on the evening before each visit, in addition to their normal dietary intake. When they arrive on the ward in the morning, two pink (20G) intravenous cannulaewill be inserted – one in each arm.

The infusion rate will be calculated according to body surface area, with the dose of glucagon based on our previous published experience of administering the hormone³. The expected maximum glucagon dose will be up to an equivalent of 100 ng/kg/min. To minimise peptide adsorption to syringes and infusion lines, the vehicle for intravenous infusions will be Haemaccel, or an equivalent safe colloid,diluted with 0.9% saline. The infusion will last 90 minutes. During the course of each study visit the volunteer will undergo serial venous blood samples. There will be a maximum of ten 8 ml samples taken per visit. These will be tested for circulating hormones, glucose and other metabolites. Over the course of the seven studyvolunteers will donate no more than a total of 560ml of blood. At regular time points, the volunteers will also be asked about their general wellbeing. Heart rate and blood pressure will be measured periodically using conventional ward equipment.

BAT in humans has been reliably demonstrated to be activated by exposure to cold temperatures. Thus, cold exposure can be used as a positive control method. We will do this by placing the volunteers' hands in a bowl of cool water or using a cooling vest for the duration of the infusion. We will ensure that the volunteer does not become uncomfortably cold, since we specifically want to avoid shivering. The cooling vest will be a commercially available unit that can be comfortably worn on the torso (as pictured below). The vest has integrated tubing through which cold water can be pumped to cool the volunteer. Temperatures can be accurately controlled using a thermostat on the water pump, and we are aiming to cool the volunteer comfortably. If the volunteer starts to shiver or is uncomfortable will will raise the temperature or remove the vest immediately.

Details of Indirect Calorimetry

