After the acclimatisation period and acquisition of control images, study images will be acquired continuously for 10 minutes prior to the start of the infusion. End-infusion study images will be acquired continuously during the last 10 minutes of the infusion. The visit protocol for Visits 1, 2 and 3 is outlined in Figure 1.

From each thermal image stream, using existing methodology², the maximal temperature over defined regions of interest in the neck region will be recorded. Data will be analysed using Prism.

Figure 1 – Visit Protocol for Study Visits 1, 2 and 3 for Healthy Volunteers

Details of PET-CT

Volunteers who have demonstrated rises in EE or BAT activation in response to glucagon infusion over Visits 1-3 will be invited to attend Visits 4 and 5, to measure BAT activation using PET-CT at the Imanova Imaging Unit in Hammersmith Hospital. The study timetable for Objective 1 is shown in Figure 2.

Positron emission tomography (PET), has become a routine research tool over the past 25 years. We will use 18-fluorodeoxyglucose (¹⁸F-FDG), an analogue of glucose to measure the metabolic rate of BAT. Metabolically active brown adipocytes avidly take up glucose, and are expected to increase their metabolic rate, and therefore the uptake of both glucose and 18F-FDG following stimulation with cold or glucagon. ¹⁸F-FDG has been previously used to study BAT activation with PET⁶⁻⁸. Dynamic PET data will be collected from the upper torso and neck will be acquired, areas known to contain significant amounts of BAT. In order to quantify the PET data adequately, a low-dose CT scan of the upper torso and chest will be conducted prior to each PET scan, in order to estimate tissue attenuation of the PET signal. The ionizing radiation exposure from the two¹⁸F-FDG PET scans (maximal administration of 185MBq per scan) and two low-dose CT scans of the upper torso, is expected to be approximately 9.5mSv.

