**NCT No. NCT01935791**

## Statistical Analysis

Based on previous studies of the hormonal and cold exposure effects on human BAT activity 1, 2, we calculated that, for an equivalent rise in EE, a sample size of 4 per group (glucagon versus control) would have 95% power to detect a significant difference between the effects of cold exposure and glucagon using F-FDG PET/CT in confirmed BAT-positive volunteers. Because of safety considerations, as PET/CT scans expose healthy patients in this study to ionising radiation, we limited this study to males only and to the smallest possible sample size to answer our initial question about the differential effects of cold exposure and glucagon administration on human BAT activity for a given rise in EE.

All data were analysed using GraphPad Prism 6 software (GraphPad Software, Inc., San Diego, CA, USA). Results are presented as means ± standard error of the mean. One-way repeated measures anova with Tukey's test was used to compare differences between the three intervention groups. A p value < 0.05 was considered to indicate statistical significance.

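### The SAP asks about BAT activity at an equal rise in energy expenditure (EE), but nothing in the plan equalises the cold and glucagon rises, so the named test supports only the plain contrast between stimuli

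*SAP*

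**What the plan says.** **SAP, Statistical Analysis.** The power statement is conditional on EE: "for an equivalent rise in EE, a sample size of 4 per group (glucagon versus control"), with 95% power claimed for cold against glucagon on PET/CT in BAT-positive volunteers. The next sentence gives the question as the "differential effects of cold exposure and glucagon administration on human BAT activity for a given rise in EE". The only analysis named is a one-way repeated measures ANOVA with Tukey's test, which "was used to compare differences between the three intervention groups", at p < 0.05. The supplied text has no EE covariate, matching tolerance, equivalence margin or rule for unequal rises.

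**Protocol, preparation and stimulation details.** For cooling, "we are aiming to cool the volunteer comfortably", with shivering to be avoided. For glucagon, "The infusion rate will be calculated according to body surface area", with the dose based on previous experience. Neither is tied to an EE target.

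**Protocol, entry to the imaging visits.** Method for Objective 1 says that "only volunteers who have a demonstrable rise in energy expenditure (EE) in response to glucagon infusion will undergo PET-CT scans". Study Visits for Objective 1 has "If the volunteers have demonstrated a measurable rise in EE or BAT activation during these first 3 study visits". Details of PET-CT has "Volunteers who have demonstrated rises in EE or BAT activation in response to glucagon infusion over Visits 1-3". The safety section asks for a significant glucagon response. The four versions differ from one another, and none compares the glucagon rise with the cold rise.

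**Protocol, what is measured when.** Calorimetry is described at Visits 1-3 only: 20 minutes before the infusion and 20 minutes starting 60 minutes into it. Visits 1-3 cover saline, saline with cold, and glucagon, with thermal imaging. PET visits (4 and 5) are saline or glucagon. MRI visits (6 and 7) are cold or glucagon.

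**The concern.** That BAT activity differs between cold and glucagon at the same rise in EE is a stronger statement than that it differs between cold and glucagon as given. The first bears on mechanism: it suggests that one stimulus raises EE through BAT and the other by another route. The second could arise simply because one stimulus raised EE more.

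Repeated measures remove differences between volunteers. They do not equalise EE between conditions within a volunteer. If the rises differ, or are too imprecisely measured to tell, a reader who takes the SAP's question at face value would credit the result with the stronger meaning.

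**Working it through.** **1. The plan's own figure.** The SAP gives 4 per group and 95% power but no effect size or SD, so the figure cannot be reproduced. Working backwards with a two-sided normal approximation, the implied standardised difference is (1.960 + 1.645) × √(2/4) = 2.55. With a two-sided paired t-test it is 2.83. With the named Tukey test (3 conditions, 6 error df) it is 3.64 residual SDs. None of these carries any information about EE.

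**2. Could a BAT difference reflect only unequal EE?** Assume no stimulus effect at equal EE, and let unequal rises shift mean BAT signal between cold and glucagon by s residual SDs (assumed values, 40,000 simulated studies). Tukey declares cold different from glucagon in:

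| s | n=4 | n=16 |
|---|---|---|
| 0 | 2.2% | 2.0% |
| 1 | 12.3% | 64.4% |
| 2 | 47.2% | 99.9% |

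The test cannot separate a stimulus effect from an EE mismatch.

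**3. Could the same test on EE show that the rises were equal?** Inputs: n=4 (SAP) and n=16 to complete (Protocol, Recruitment for Objective 1). The documents do not say which applies to the Visit 1-3 EE data, so both are shown. No EE variance is given, so the unit is the SD of the paired cold-minus-glucagon difference in EE rise, with equal SDs assumed across conditions. Tukey is non-significant when |t| < q/√2, where t is noncentral with 2(n−1) df and noncentrality gap × √n.

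- n=4: q(0.95; 3, 6) = 4.339, so the critical value is 3.07. For a gap of 1 SD, the noncentrality is 1 × √4 = 2.
- n=16: q(0.95; 3, 30) = 3.486, so the critical value is 2.47. For a gap of 1 SD, the noncentrality is 1 × √16 = 4.

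| True gap in EE rise | Non-significant, n=4 | Non-significant, n=16 |
|---|---|---|
| 0.5 SD | 93% | 66% |
| 1 SD | 76% | 7% |
| 1.5 SD | 48% | under 0.1% |

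**4. How precisely can the EE difference be estimated?** The paired half-width is t/√n.

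- 95% CI: 3.182/2 = 1.59 SD (n=4); 2.131/4 = 0.53 SD (n=16).
- 90% CI: 2.353/2 = 1.18 SD (n=4); 1.753/4 = 0.44 SD (n=16).

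If that SD is 0.5 to 1 times the mean EE rise (assumed), the 90% half-width is 59-118% of the rise at n=4 and 22-44% at n=16.

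**5. Chance of showing equivalence when the rises are truly equal** (90% CI inside ± margin):

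| Margin | n=4 | n=16 |
|---|---|---|
| 0.5 SD | 2% | 24% |
| 1 SD | 20% | 97% |

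An 80% chance needs a margin of 1.94 SD at n=4 or 0.77 SD at n=16.

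**6. Does EE line up with each BAT measure?**

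| BAT measure | Conditions in the protocol | EE at the same visit? |
|---|---|---|
| PET, Visits 4-5 | saline, glucagon | not described |
| MRI, Visits 6-7 | cold, glucagon | not described |
| Thermal imaging, Visits 1-3 | saline, cold, glucagon | yes |

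The infusion lasts 90 minutes and the end-infusion thermal images take its last 10, so they fall at minutes 80-90, directly after the EE window at minutes 60-80. Thermal imaging is also the only BAT measure with all three conditions in the protocol.

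**The case against.** **It is a planning assumption.** The power statement can be read that way, and that reading is fair for the sentence on sample size. It does not cover the next sentence, where equal EE is part of the question. The SAP states no EE-conditional conclusion, however, so the harm lies in how results would be read, not in a claim already made.

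**EE is measured under all three conditions, so it can be compared.** True, and the comparison is worth reporting. Steps 3 to 5 show why it cannot serve as proof of equality, above all at n=4.

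**The figures are in SD units.** This stands. They show how weak an EE check would be. They do not measure bias in the BAT contrast.

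A reader might also infer more than the documents support:

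- *That the EE rises actually differed.* Nothing in the documents shows this.
- *That EE was measured later than most of the PET scan.* The protocol starts the infusion, moves the volunteer to the scanner and then gives the tracer, but states no interval. If the 60-minute scan began between minutes 20 and 30, the whole EE window would fall inside it.
- *That no BAT measure can be linked to EE.* Thermal imaging shares the visits and conditions.
- *That passing an EE equivalence test at Visits 1-3 would justify the wording for PET or MRI.* It would show only similar mean rises at other visits, not matching during the scans or within each volunteer.

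**Conclusion.** The point holds as a mismatch between question and analysis. The plan as written supports the contrast between cold and glucagon as given, and not a contrast at equal EE. That contrast remains usable; only the EE-conditional wording is unsupported.

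A non-significant EE comparison would not rescue the wording: with a true gap of 1 SD it occurs in 76% of studies at n=4 and 7% at n=16. This rests on equal SDs across conditions, and its practical size depends on an EE variance that the documents do not give.

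The absence of a matching rule is judged on the supplied text, since part of the SAP was removed before review. Confidence is medium. The change should be made because it alters what can be concluded.

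**What to change.** 1. State the main result as the unconditional cold-glucagon contrast and name the BAT modality it comes from. The SAP is sized on cold against glucagon by PET/CT, while the protocol describes no cold condition at the PET visits, so these passages must be reconciled first.
2. Beside it, report the paired Visit 1-3 cold-minus-glucagon difference in EE rise (minutes 60-80 minus the pre-infusion measurement) with 90% and 95% CIs and the n used. Present it as a description of how similar the mean rises were, not as proof that they matched.
3. For PET and MRI, drop the EE condition from the question. In the power statement, label it an untested planning assumption. Say that no calorimetry is described at Visits 4-7 and that the interval from infusion start to PET scan is not stated.
4. For thermal imaging, keep EE-conditional wording only if the 90% CI lies inside a margin justified independently of the results, and then only as similarity of mean rises. The SAP is written in the past tense, so a margin chosen now from these data would not qualify.
5. Do not adjust for EE as a simple covariate. It is measured after the stimulus starts and may itself result from BAT activation.

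The cost is SAP wording and one interval on data already collected, with no extra visit, scan or model. The downside is that the EE-conditional wording is lost for PET and MRI even if the rises were truly equal. For thermal imaging with truly equal rises, it would be lost in 80% of studies at n=4 and 3% at n=16 under a 1 SD margin, and in 98% and 76% under a 0.5 SD margin.

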At each PET-CT visit two intravenous cannulae will be inserted into the forearm or cubital veins in order to administer the ¹⁸F-FDG and glucagon or saline infusion (via one cannula), and collect blood samples during the course of the PET-CT scans (via the second cannula). The glucagon or saline infusion will be initiated and then the volunteers will be then be led into the scanner room where the 18F-FDG bolus will be administered immediately prior to the scan. Subjects will undergo a brief low dose CT followed by a 60-minute dynamic PET scan. Volunteers will be lying on a bed throughout the scan and can communicate with (and will be reassured by) the radiographer and researchers as necessary.

[figure not shown]
Images will be quantified by deriving standard outcome parameters for the defined regions of interest, using established methodology. All of the PET-CT scans will also be formally reported by a consultant radiologist. Although the PET-CT scans are not performed with the aim of clinical diagnosis, and this may not be considered of diagnostic quality, they may reveal an incidental finding relevant to the subjects health status. In this situation the report would be communicated to the volunteer and the volunteer's GP, who would arrange the appropriate specialist referral. A significant abnormality would exclude that volunteer from further participation in the study.

Figure 2 – Study Timetable for Objective 1

OBJECTIVE 1: To assess BAT activation in response to glucagon infusion in healthy volunteers using PET-CT and thermal imaging.

N=16 healthy male volunteers to complete this arm

- NB. - Visits 1-3 will be allocated in a random order.
 - Visits 4 to 7 will only be undertaken if there has been a demonstrable response to glucagon infusion over Visits 1-3.
 - All infusions will be single-blinded.

Details of MRI

Volunteers who have successfully completed visits 1-5 will also be invited to attend Visits 6 and 7. The objective of these visits is to measure BAT activation using MRI at the Imanova Imaging Unit, Hammersmith Hospital.

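### Objective 1 randomises visit order, but no balancing is stated and the SAP's model has no visit term, so drift across visits, if present, would cost precision

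*SAP*

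**What the plan says.** The protocol (Study Visits for Objective 1) gives each volunteer saline at thermoneutrality, saline with cold, and glucagon over Visits 1-3. Those who respond go on to saline or glucagon with PET-CT at Visits 4-5, then saline with cold or glucagon with MRI at Visits 6-7. Each set is "allocated in a randomised single-blinded fashion", and the notes to Figure 2 add that "Visits 1-3 will be allocated in a random order". No sequence list, block size or Latin square is given. On spacing the protocol says "There will be a time interval of at least two days between visits", with no upper limit.

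The SAP (Statistical Analysis) gives one model, "One-way repeated measures anova", with Tukey's test for the differences among three interventions. It adds "A p value < 0.05 was considered to indicate statistical significance". Its sample size statement is that "a sample size of 4 per group (glucagon versus control) would have 95% power", for PET/CT. The protocol's Recruitment section plans 20 recruited and 16 completing.

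**The concern.** Seven visits with cannulae, a calorimeter canopy and scanners, spread over an open-ended schedule, leave room for responses to change with visit number. A crossover that randomises order can remove such a change at little cost by spreading the orders evenly and fitting visit in the model. Here the documents commit to neither step. In a sample of 16, or of 4, chance can leave the orders uneven, and a residual enlarged by drift weakens the glucagon comparisons.

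**Working it through.** **Inputs.** From the documents: 16 completers (protocol); 4 per group at 95% power and significance at 0.05 (SAP; two-sided assumed); a one-way repeated measures model with Tukey's test (SAP). Assumed, because the documents give no figure: linear drift of L within-person SDs per visit, with L from 0 to 1.0; simple randomisation where a result is labelled so; and the true effects used for power.

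**The plan's own figure.** The SAP gives no effect size or SD, only that the calculation is "Based on previous studies of the hormonal and cold exposure effects on human BAT activity", so 4 per group cannot be reproduced. Solving backwards for 95% power at n = 4, two-sided, gives a standardised difference of 2.55 (normal approximation), 3.09 (two-sample t) or 2.83 (paired t).

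**Residual inflation, Visits 1-3.** Positions 1, 2, 3 deviate from their mean by -1, 0, +1. Each man therefore adds 2L² to the within-person sum of squares on 2 degrees of freedom, and the residual variance is multiplied by 1 + L²:

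- L = 0.25: 1.0625, up 6%
- L = 0.5: 1.25, up 25%
- L = 1.0: 2.00, up 100%

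**SD of a condition difference under simple randomisation.** For one man the positions of two conditions differ by 1 with probability 2/3 and by 2 with probability 1/3, so the mean square is 2/3 + 4/3 = 2. The variance of the estimated difference is 2(1 + L²)/n. At n = 16 the SD is √(2/16) = 0.354 with no drift, 0.354 × 1.118 = 0.395 at L = 0.5, and 0.354 × 1.414 = 0.50 at L = 1.0. The order-imbalance part alone has SD L√(2/n): 0.35L at n = 16 and 0.71L at n = 4. Two conditions differ by at least half a visit in mean position in 19% of draws at n = 16 and 62% at n = 4.

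**Two-visit pairs under simple randomisation.** With 16 men, a split of 10:6 or worse has probability 29786/65536 = 0.454. At 10:6, (10 - 6)/16 = 0.25 of any period effect enters the unadjusted difference. With 4 men, a 2:2 split has probability 6/16 = 37.5%, and all four fall in one order with probability 2/16 = 12.5%.

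**Power for one Tukey pair.** These are simulations of 4,000 trials per scenario, with Monte Carlo error up to about 0.8 points. The true effect is 1.12 within-person SD at n = 16 and 18, and 2.9 at n = 4, chosen for illustration. Order is simply random at n = 16 and n = 4; at n = 18 all six orders are used equally.

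| L | n=16, no visit term | n=16, visit term | n=18, no visit term | n=18, visit term | n=4, no visit term | n=4, visit term |
|---|---|---|---|---|---|---|
| 0 | 76% | 72% | 82% | 82% | 81% | 57% |
| 0.5 | 64% | 71% | 73% | 81% | 72% | 57% |
| 1.0 | 41% | 71% | 46% | 82% | 48% | 56% |

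**Degrees of freedom.** At n = 16 the error df are 15 × 2 = 30, falling to 28 with a visit term. At n = 4 they are 3 × 2 = 6, falling to 4; the Tukey critical value rises from 4.34 to 5.04, and the term could not be fitted in about 10% of random draws.

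**Validity.** With no true effect, mean bias was about 0. Under random order without the visit term, the rejection rate per Tukey pair was about 2% at n = 16 and 2.5% at n = 4, with or without drift.

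**The case against.** The strongest reply is that this is about efficiency and rests on drift that nobody has documented. Much of that stands.

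- **Silence is not imbalance.** A reader might infer that order was left unbalanced. The documents say only that it was random, and blocked or Latin-square allocation is random too. The figures for simple randomisation are conditional on that method.
- **No bias.** A reader might infer that uneven orders bias the glucagon effect or produce false positives. Averaged over the randomisation they do neither. Under simple randomisation the wider spread of the estimate is matched by the larger residual: both scale with 1 + L², so they are one loss and should not be counted twice.
- **Not every drift matters.** The protocol's first outcome is a change from the unstimulated state. Energy expenditure has a 20-minute reading before infusion and thermal imaging a 10-minute one. If that change is analysed, a shift in a visit's overall level cancels and only drift in the response remains. The SAP does not say which scale is used. PET lacks this protection: the infusion starts before tracer and scan.
- **The remedy can cost power.** With no drift, the visit term loses about 4 points at n = 16. At n = 4 it loses power at L = 0 and 0.5 and gains only at L = 1.0.

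What remains is that neither document commits to balanced order or to a visit term, and at n = 16 the small premium insures against a loss that could reach about 30 points (41% against 71% at L = 1.0).

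**Conclusion.** The point holds as a worthwhile, inexpensive improvement. No balancing is stated and the named model cannot remove a visit effect. If responses drift, residual variance rises by 6%, 25% or 100% at an assumed 0.25, 0.5 or 1.0 within-person SD per visit, and a realised order imbalance goes unadjusted. With no drift nothing is lost. The size rests wholly on the assumed drift, and the imbalance figures also assume simple randomisation. The documents do not support a claim of systematic bias or inflated type I error. PET is the most exposed measure, and also the one the SAP's sample size addresses.

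**What to change.** 1. **Allocation.** State the method. For Visits 1-3, use a pre-generated list with the six sequences spread as evenly as n allows. Exact balance is impossible at 16 or 20, since neither divides by 3; 18 would fit. For the PET and MRI pairs, allocate in small blocks so that the two orders are as equal as possible among those who enter, because entry depends on earlier visits and the number is not fixed.
2. **Analysis at about n = 16.** Fit visit number as a fixed effect with volunteer as a random effect. Balance alone does not suffice: at n = 18 with equal orders and L = 1.0, power is 46% without the term and 82% with it. The cost is 2 of 30 df for Visits 1-3 and 1 of 15 for a two-visit pair.
3. **Analysis at about n = 4.** Rely on balanced order and report the visit-adjusted estimate only as a sensitivity analysis, since for three visits the term takes 2 of 6 df. Balance protects the estimate here, but drift would still sit in the residual.
4. **If allocation is complete.** The SAP is written in the past tense. Report the realised orders and apply the same rule by sample size; this needs no new data.
5. **PET.** Reconcile the SAP, which compares three interventions and refers to cold versus glucagon on PET/CT, with the protocol's two-visit saline/glucagon PET pair, and name the PET model. State also whether change from the within-visit baseline is the analysed scale for energy expenditure and thermal imaging.
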